#### **1.1 Background/Significance**

The vagus nerve (VN) provides a bidirectional link between the brain and the gastrointestinal tract, and as such, is involved in maintaining the homeostasis of gut functions such as sensitivity, motility, and immunity both through its sensing and modulatory roles (Matteoli & Boeckxstaens 2013). The VN classically innervates the digestive tract from the esophagus to the splenic flexure, however for some anatomists, the VN innervates all the digestive tract in human. Dysfunction of the vagal tone has been observed in functional and inflammatory digestive disorders (Bonaz et al 2016 Rev). Being a major component in the control of upper gastrointestinal motility, low vagal tone has been associated with gastrointestinal motility disturbances (Bonaz et al 2016 Rev).

Gastroparesis is a disorder associated with delayed gastric emptying in the absence of mechanical obstruction. Patients with gastroparesis are often malnourished and experience a range of symptoms from nausea, vomiting, postprandial fullness, early satiety, and abdominal pain leading to significantly compromised quality of life and economic burden (Wang et al 2008; Talley et al 2001). Implicated etiologic factors include diabetes mellitus, although a third of the cases are idiopathic. Physiological vagal input to cholinergic enteric neurons is necessary to maintain a basal gastric tone and is important for gastric accommodation in humans (Lunding et al 2008; Azpiroz & Malagelada 1987). Antral dysmotility is a consistent finding in diabetics with delayed gastric emptying and impaired gastric autonomic innervation probably contributes to this dysmotility. An additional layer of complexity is provided by the fact that the digestive tract is exposed to a variety of luminal signals derived from the microbiota (Guarino et al 2016). Beyond the well-documented effects on gut immune responses, recent data suggest that dysbiosis of gut microbiota can affect gastrointestinal motility (Guarino et al 2016), although this has not been studied in gastroparesis.

Inflammation is increasingly recognized as playing an important role in gastrointestinal motility disorders such as gastroparesis (Spiller & Major 2016). Immune

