## **3 Study Design**

### **3.1 General Design**

This is a prospective interventional pilot study assessing the safety and tolerability, as well as efficacy of the use of VNS in patients with idiopathic and functional gastroparesis. We will also include patients with functional dyspepsia, which have almost identical clinical symptomatology and are believed to share similar underlying inflammation and dysautonomia. We plan to recruit a total of 45 patients, 15 patients of each subgroup, for 4 weeks of therapy with VNS. Patients will undergo baseline measures of symptoms, gastric emptying testing, vagal tone, and inflammation. After enrollment, patients will undergo two upper endoscopies (pre and post therapy). Pt will be seen in clinic for recruitment, day 0, for follow-up at 4 weeks, and again at 8 weeks, for a total of six visits including their appointed endoscopy days.

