### **3.2 Study Objectives**

1. Establish the effect of VNS on gastric emptying time and on cardinal symptoms of gastroparesis (nausea, vomiting, bloating, abdominal pain, and early satiety).
2. Assess the effects of VNS on various measures of quality of life, including global health and overall pain interference.
3. Investigate molecular and neuroimmune signaling pathways in different gastroparesis patients.
4. Determine the effects of VNS on measurable serum inflammatory markers and cytokines.
5. Determine the effects of VNS on measurable cytokines, nerve growth factors, and neurotransmitters in the gastric and duodenal submucosa.
6. To characterize the submucosal enteric nervous system in gastroparesis subtypes and identify novel neuro-immune interactions.
7. Determine if gastric emptying and symptom response to VNS is associated with changes in inflammatory markers and neuro-immune signaling.
8. Determine if there is a difference in response to VNS in patients with idiopathic vs. diabetic gastroparesis.
9. Evaluate the safety and tolerability of VNS therapy in patients with gastroparesis and functional dyspepsia.

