#### ***4.2 Sample size justification***

- Total of 45 patients; 15 with functional dyspepsia, 15 with diabetic gastroparesis, and 15 with idiopathic gastroparesis.
- Primary comparison: Gastric emptying half time score and GCSI, pre and post VNS
- Error protection: Type I = 0.05 two-sided and Type II = 0.10 (80% power). To detect a clinically significant change of >30% in gastric emptying time, and a reduction in  $\geq 1$  GCSI aggregate.

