## **7. Statistical Analysis Plan**

The mean baseline GCSI aggregate score will be compared with the mean aggregate score at the end of each treatment week, and in the 4 subsequent weeks after therapy discontinuation. Paired Student T-tests will be done comparing baseline with all other subsequent time points. Gastric emptying times will be plotted before treatment, at the end of treatment, and four weeks after end of treatment and compared by ANOVA. Similarly, differences among the three subgroups of patients will be determined at baseline and after treatment.

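### Section 7 states no analysis for Objective 8: its only subgroup rule compares three diagnoses at separate times and never estimates the idiopathic versus diabetic difference in response

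*Combined protocol and SAP*

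**What the plan says.** Section 3.2, item 8, sets a two-group question about response: "Determine if there is a difference in response to VNS in patients with idiopathic vs. diabetic gastroparesis".

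Section 3.1 fixes the group sizes: "We plan to recruit a total of 45 patients, 15 patients of each subgroup, for 4 weeks of therapy with VNS". The third group, functional dyspepsia, is not part of Objective 8.

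Section 7 has one sentence on subgroups, which states that "differences among the three subgroups of patients will be determined at baseline and after treatment". It opens with *Similarly* and follows the gastric emptying sentence: "Gastric emptying times will be plotted before treatment, at the end of treatment, and four weeks after end of treatment and compared by ANOVA". The GCSI analysis in the same section is a set of within-patient paired t-tests with no group term.

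Section 4.2 sizes the trial for the within-patient question only: "Primary comparison: Gastric emptying half time score and GCSI, pre and post VNS". No endpoint in Section 3.3 compares response by subtype, and no other section defines response for Objective 8 or gives a test for it.

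**The concern.** A difference in response is a difference between two changes. The subgroup sentence gives two snapshots instead, one before and one after therapy, each across three groups that were formed by diagnosis and not by randomisation. Two things are missing.

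- **The estimate.** An after-treatment difference between diagnoses mixes any difference that was already there with any difference in response. Testing each time point separately does not separate them.
- **The pair.** A three-group test, whether at one time or as an interaction, can be significant because of functional dyspepsia alone.

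If these comparisons were taken as the answer to Objective 8, a pre-existing gap could be reported as a difference in response, or a real difference could be hidden. With no contrast fixed, the choice among after-treatment values, an interaction, raw change and percentage change also stays open until the data are seen.

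**Working it through.** **Inputs from the documents.** There are 15 patients per diagnosis (Sections 3.1 and 4.2) and a two-sided alpha of 0.05 (Section 4.2). Section 4.2 states a Type II error of 0.10 next to 80% power, so both power levels are shown where it matters.

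**Assumed inputs, because the documents give none.** Outcome SD is 1 at each time, the pre-post correlation ρ is 0.5 or 0.7, and the idiopathic minus diabetic baseline gap g is 0, 0.25, 0.5 or 1 SD.

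**The plan's own figure.** The 45 patients cannot be reproduced, because no SD of change is given. By paired t, 15 per subgroup would detect 1 GCSI point if the SD of change is at most 1.29 (80% power) or 1.11 (90%). This concerns the pre-post question and not Objective 8.

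**1. What each comparison estimates.** Let r be the idiopathic minus diabetic difference in change, and let the gap be stable.
- Baseline difference = g
- After-treatment difference = g + r
- Difference in change = (g + r) − g = r

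The after-treatment difference equals r only when g = 0.

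**2. Equal response (r = 0), 15 vs 15 after treatment.** The noncentrality is g × √(15/2) = 2.739g on 28 df.

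| Assumed stable gap | Noncentrality | After-treatment test rejects | Change rejects |
|---|---|---|---|
| 0 | 0 | 5% | 5% |
| 0.25 SD | 0.68 | 10% | 5% |
| 0.5 SD | 1.37 | 26% | 5% |
| 1 SD | 2.74 | 75% | 5% |

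In simulation (40,000 replicates), the three-group ANOVA after treatment rejects 5%, 8-10%, 20-26% and 65-79% for the same gaps. The range reflects whether the third group sits at the lower mean or midway.

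**3. Masking.** Take g = 0.5 and r = −1. The after-treatment difference is 0.5 − 1 = −0.5 SD, detected about 26% of the time. The SD of change is √(2(1 − ρ)), which is 1.00 at ρ = 0.5 and 0.775 at ρ = 0.7. The standardised difference in change is therefore 1.00 or 1/0.775 = 1.29, and its power is 75% or 92%.

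**4. A three-group test does not isolate the pair.** Suppose only functional dyspepsia differs, by 1 SD: means 0, 0, 1. Then λ = 15 × Σ(m − m̄)² = 15 × 2/3 = 10, and F on 2 and 42 df rejects about 78%. Under the subgroup-by-time reading, a dyspepsia response that differs by 1 SD makes the interaction significant in 78% (ρ = 0.5) or 95% (ρ = 0.7). The idiopathic versus diabetic contrast of change rejects 5% in both cases.

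**5. Limits of the proposed contrast.**
- Detectable difference, 15 vs 15: 1.06 SD of change at 80% power and 1.23 at 90%. Power is 26% at 0.5 SD of change.
- 95% CI half-width: t(0.975, 28) × √(2/15) = 2.048 × 0.365 = 0.75 SD of change.
- The variance of change is 2(1 − ρ) and exceeds 1 when ρ < 0.5. With no gap and a correlation that low, change is less precise than the after-treatment comparison.
- If the gap partly regresses (after-gap = ρg), change falsely rejects 8-10% at a 0.5 SD gap and 17-26% at 1 SD, while baseline adjustment holds 5%. If the gap is stable, change holds 5%, while baseline adjustment rejects 8-11% and 17-27%.
- Scale for gastric emptying, with assumed means of 115 or 130 vs 100 and SD 30: under an equal 30% shortening, raw change falsely rejects 7-9% or 14-21%. Under an equal 30-unit shortening, log change falsely rejects 8-10% or 16-22%.

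**The case against.** Several points on the other side stand.

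- **Standing of the objective.** Objective 8 is tied to no primary, secondary or exploratory endpoint, the trial is a pilot, and Section 7 is equally brief on most other objectives. This limits the weight of the point, but a listed objective still has no stated analysis.
- **The charitable reading.** *Similarly* follows an ANOVA over time, so a subgroup-by-time model may be meant. It is not stated, and it would still test three groups.
- **The consequence needs a further step.** A reader might infer that the plan will produce false positives for Objective 8. The documents do not support that. Section 7 never says that the three-group comparison is the test of Objective 8, and a three-group test that detects a true dyspepsia difference is not a false positive for its own hypothesis. The planned baseline comparison would also display a gap, although 15 against 15 would often miss one of 0.5 SD.
- **No gap is documented.** A reader might infer that the diagnoses start at different levels. No figure is given for any pair. On symptoms, Section 3.1 points the other way: "We will also include patients with functional dyspepsia, which have almost identical clinical symptomatology". On emptying, Section 1.1 says "Gastroparesis is a disorder associated with delayed gastric emptying in the absence of mechanical obstruction", so a gap between dyspepsia and gastroparesis is plausible. That remains an inference, and it does not concern the Objective 8 pair.
- **Change is not the only defensible estimate.** Baseline adjustment does better if a gap regresses and worse if it is stable. Neither dominates in non-randomised groups, and the documents do not decide between them.

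**Conclusion.** The point holds as a gap in the analysis plan. Followed literally, Section 7 never estimates the idiopathic versus diabetic difference in response, and under either reading its subgroup test does not isolate that pair.

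The rejection rates of 26% and 75% against 5% are illustrations. They rest on assumed stable gaps of 0.5 and 1 SD, and with no gap the after-treatment comparison is valid. They are not predictions for this trial.

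A reader might also infer that the main results are compromised. They are not: the primary comparisons are within-patient and do not use the subgroup rule. The change is worth making because one stated objective lacks an analysis and a few sentences supply it.

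**What to change.** Add to Section 7:

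> For Objective 8, the idiopathic versus diabetic difference in change from baseline to end of treatment (subgroup-by-time contrast for this pair) will be estimated for GCSI and for gastric emptying half time (as a ratio to baseline), with a 95% CI, and labelled exploratory. A baseline-adjusted estimate is a sensitivity analysis. The separate three-group comparisons before and after therapy are descriptive and are not the test of response.

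The ratio scale matches the percentage target in Section 4.2 ("To detect a clinically significant change of >30% in gastric emptying time"). No scale is safe under both effect models, so the choice should be fixed in advance and raw change reported as a sensitivity analysis. The sponsor may instead make the baseline-adjusted estimate the main one, provided that one is fixed beforehand.

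**Cost.** The change is wording only. The contrast uses measurements already scheduled at baseline and end of treatment. The GCSI baseline window must be named, because the assessment list gives one week and the schedule table two weeks before VNS.

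A follow-up contrast should be added only after the timing is reconciled. Section 5.2 and Section 7 refer to four weeks after therapy stops. The schedule table ends the GCSI diary two weeks after VNS and puts the washout visit at Day 51, which is 51 − 28 = 23 days after Day 28. The assessment list gives gastric emptying only at baseline and after therapy.

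**Downside.** The estimate will be imprecise, with a CI half-width of about 0.75 SD of change. With non-randomised groups and no untreated arm, a difference in change can also reflect regression to the mean, which is a further reason for the exploratory label.

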## **Appendix**

[figure not shown]
### **I. Layman's Narrative of Project:**

Gastroparesis is thought to be caused by a mix of inflammation and neural dysfunction. The vagus nerve is a large nerve originating from the brain, which innervates the stomach and intestine, and plays a key role in maintaining normal gastrointestinal function. Research shows that a high vagal tone makes your body better at regulating blood glucose levels, reducing the likelihood of diabetes, stroke and cardiovascular disease. Low vagal tone, however, has been associated with chronic inflammation. Research also shows that patients with gastrointestinal motility problems, such as gastroparesis, have a low vagal tone. Further, in animal models, stimulation of the vagus nerve can have an anti-inflammatory effect in the the bowels, and improve gastrointestinal motility. Stimulation of the vagus nerve is an FDA-approved therapy for seizures and depression, but it has not been studied carefully in patients with gastroparesis. In this study, our aim will be to improve gastric motility and measures of inflammation by vagal nerve stimulation. We will stimulate the vagus nerve using a hand-held device which every study subject will be trained to use in their home. Stimulations will last only a few minutes and will be conducted twice a day for total duration of 4-8 weeks. To evaluate the potential benefits of vagal nerve stimulation, we will assess gastric emptying and inflammation by routine, standard of care tests such as upper endoscopy, breath testing, and sampling of blood, stool, urine, and saliva. We will also measure autonomic dysfunction via the Ansan autonomic functioning machine and the Heart Rate Variability Camera App. A recent autonomic evaluation of gastroparesis patients undergoing neurostimulation suggests that heart rate variability and systematic autonomic testing are both reliable methods of measuring autonomic changes before and after neurostimulation (Stocker et al, 2016). Utilizing mobile apps to measure heart

rate variability has been reliably tested (Scully et al 2012), and preliminary results from our studies specific mobile app suggests that the specific technology of photoplethysmography has provided accurate and non-invasive cardiac measures that can be integrated into research settings. ( Altini et al, 2017; Plews et al 2017)

[figure not shown]
**II. Gastric Emptying Breath Test (GEBT)** is a non-radioactive, non-invasive, orally administered test for measurement of the rate of solid phase gastric emptying in adults. The GEBT has been validated against the reference method of gastric scintigraphy.

### **III. gammaCore VNS device:**

Images provided courtesy of electroCore, LLC.

